	3.2.1, 3.2.2	Added the inclusion of dichorionic diamniotic twin gestations in which only one fetus has an eligible anomaly. Monochorionic diamniotic (MCDA) and monochorionic monoamniotic (MCMA) twins and a gestation in which both fetuses have an anomaly are excluded.	Improve generalizability of the results by including twin gestation. MCDA and MCMA are excluded due to the increased risk of adverse pregnancy outcomes.
	3.2.1.2, 3.2.2.2	Updated exclusion criteria to eliminate the need for delivery at a study center or associated hospital	This will allow enrollment of individuals who deliver at outside hospitals
	4.2.1	Clarified that either the twin with the anomaly or both twins will be sampled according to local clinical practice	The study only requires the twin with the anomaly to be sampled, but some sites sample both as part of clinical practice
	4.3	Clarified that data collection will include twin gestation	This will be collected in order to account for twin gestations
	4.5	Clarified that the reporting of secondary fetal findings will be per local site guidelines	This will allow sites to report secondary fetal findings during pregnancy
	4,6, 4.8	Clarified that for twin gestations, neonatal and cost data will only be collected for the twin with the anomaly	Outcomes will only be analyzed for the fetus with the anomaly

Date	Affected Section(s)	Summary of Revisions Made	Rationale
18 May 2021	3.2.1.2	Clarified exclusion criteria for the sequenced group so that only those with positive gene panels are excluded	This will allow those patients with negative gene panels to be included which could benefit from whole genome sequencing
	3.2.2.2	Clarified that CMA findings that are pathogenic or likely pathogenic as well as causal are excluded	Pathogenic or likely pathogenic variants that are related to the prenatal ultrasound finding will be excluded
	4.1	Updated eligibility flow chart to reflect changes to sample collection	Maternal buccal swab/saliva or blood may be collected
	4.2.1	Added that maternal buccal swab/saliva may be collected instead of blood	There are times when collecting blood is not feasible, and DNA can be extracted from either blood or saliva
	4.7.1	Clarified that there will be one interview between 2 weeks after results disclosure or 4 weeks after enrollment for the unsequenced group and 15 months after delivery	Each parent will be interviewed once, and the interview will be scheduled at some point during study follow-up

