#### 3.2.1.2 Exclusion Criteria

- 1. Imminent delivery planned (within 3 weeks of enrollment) as sequencing results would not be available prior to delivery
- 2. Prenatal sequencing or planned prenatal sequencing performed outside of the study. Gene panels may be performed prior to enrollment but the results must be known and negative to be eligible (positive or unknown results are an exclusion).

- 3. Maternal or paternal age less than 18 years old
- 4. Proven infectious, teratogenic, or other genetic cause of fetal anomaly
- 5. For twin gestation, anomalies in both fetuses (NT, IUGR, or structural anomaly)
- 6. Monochorionic diamniotic (MCDA) and monochorionic monoamniotic (MCMA) twins as well as higher-order multifetal gestations
- 7. Planned termination of the fetus or intrauterine fetal demise (IUFD)
- 8. Unavailable blood or saliva samples from both genetic parents prior to sequencing
- 9. Parental unwillingness to participate in 1 year postnatal follow-up
- 10. Language barrier (non-English or Spanish speaking)
- 11. Previous consent to the unsequenced prenatal group or enrollment in a previous pregnancy

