#### 3.2.2.2 Exclusion Criteria

- 1. Prenatal or postnatal (prior to neonatal discharge) CMA with pathogenic or likely pathogenic variants that are related to the prenatal ultrasound finding
- 2. Maternal or paternal age less than 18 years old
- 3. Proven infectious, teratogenic, or other genetic cause of fetal anomaly
- 4. Positive prenatal NIPT screening for trisomy 21, 18 or 13. Positive 22q11.2 prenatal NIPT testing with consistent ultrasound findings is also an exclusion.
- 5. For twin gestation, anomalies in both fetuses (NT, IUGR, or structural anomaly)
- 6. Monochorionic diamniotic (MCDA) and monochorionic monoamniotic (MCMA) twins as well as higher-order multifetal gestations.
- 7. Planned termination of the fetus or intrauterine fetal demise (IUFD)
- 8. Unable to consent both genetic parents
- 9. Parental unwillingness to participate in 1 year postnatal follow-up

10. Language barrier (non-English or Spanish speaking)

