#### 3.2.3.2 Exclusion Criteria

- 1. Prenatal or postnatal (prior to neonatal discharge) CMA with pathogenic or likely pathogenic variants that are related to the prenatal ultrasound finding
- 2. Maternal or paternal age less than 18 years old
- 3. Proven infectious, teratogenic, or other genetic cause of fetal anomaly
- 4. Positive prenatal NIPT screening for trisomy 21, 18 or 13. Positive 22q11.2 prenatal NIPT testing with consistent ultrasound findings is also an exclusion.
- 5. For twin gestation, anomalies in both fetuses (NT, IUGR, or structural anomaly)
- 6. Monochorionic diamniotic (MCDA) and monochorionic monoamniotic (MCMA) twins as well as higher-order multifetal gestations.
- 7. Termination of the fetus or intrauterine fetal demise (IUFD) within 3 weeks of date of initial anomaly diagnosis
- 8. Language barrier (non-English or Spanish speaking)
- 9. Delivery at a site other than one of the study centers or associated hospitals
- 10. Unable to access prenatal or neonatal records

[figure not shown]

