#### 5 Statistical Considerations

# 5.1 Power and sample size

The first primary outcome for this study is the frequency of pathogenic, likely pathogenic, or VUS genomic variants identified by sequencing among participants with a normal karyotype and CMA. The sample size is based on the incremental yield reported in a prospective study of WES performed at Columbia University in a similar population. Among 234 parent-fetus trios without CMA abnormalities, a genetic diagnosis was reported in 22 (9.4%). The precision of the estimate for a range of sample sizes and estimates is shown in Table 4. An estimate of 9.4% and sample size of 750 in the prenatal sequenced group will have a precision of 2.3% (confidence interval half-width) with a 93% probability.

Estimate	Sample size	Cl ½-width
9.0%	700	2.4%
	750	2.3%
	800	2.2%
9.4%	700	2.4%
	750	2.3%
	800	2.3%
9.8%	700	2.5%
	750	2.4%
	800	2.3%

The second primary outcome is maternal and neonatal hospital charges. The utilization of health care and cost only will include women that deliver at one of the study centers. Given that some of the recruiting centers include referrals in which the women will not deliver at the study center, power estimates assume cost will be available on 500 of the 750 in the prenatal sequencing group. Similarly, of the 350 unsequenced prenatal controls, 15% are assumed to have a pathogenic or likely pathogenic causal pre-/postnatal CMA prior to neonatal discharge or deliver elsewhere resulting in approximately 300 unsequenced prenatal controls available for analysis. The total charges for deliveries at Columbia University that required a NICU admission in 2016 and 2017 (partial year) were used to provide cost estimates. The charges follow a lognormal distribution approximately with a mean total charge of \$277,902 and standard deviation of \$389,484. Assuming 500 participants in the prenatal WGS group, and 300 unsequenced prenatal control participants, the study will have 80% power to detect a mean ratio of 0.80 (20% reduction) with an alpha=0.05 two-sided.

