## 5.3 Prenatal Sequencing and Prenatal Unsequenced Groups

Clinical management including health care utilization and cost, and pregnancy and neonatal outcomes will be compared among the prenatal sequencing group and the unsequenced prenatal group (prospective and retrospective). Women whose fetus or neonate is found to have pathogenic or likely pathogenic causal findings on CMA prior to neonatal discharge will be excluded from these analyses. Twelve month postpartum outcomes will be compared only among those individuals enrolled prospectively. Initially, demographic data and severity of ultrasound findings will be compared to ensure there are no significant differences between the two study groups (prenatal sequencing and unsequenced prenatal group). If differences are found, the covariates will be adjusted for in the analyses.

Categorical variables will be reported as the number and frequency and associations assessed by the Pearson's chi-square or Fisher's Exact test. The distributions for continuous variables will be assessed for normality and transformed to fit a normal distribution if possible. Normal distributions will be reported as mean and standard deviation and compared with the t-test, and non-normal data will be reported as median and interquartile range and compared with the Mann-Whitney U test.

For each outcome, if the study groups show a significant difference, interactions will be tested and subgroup analyses conducted if the interaction is significant (p<0.05). Pre-specified subgroup analyses include maternal age, race/ethnicity, fetal sex, and type of anomaly (lethal vs non-lethal).

The amount of missing data, missing data patterns, and identification of variables associated with missingness will be explored to inform the primary and sensitivity statistical analyses. Analytic techniques used to address missing data bias will be used as appropriate. A two-sided nominal p-value less than 0.05 will indicate statistical significance.

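### Only retrospective controls must deliver at a study center or associated hospital, yet section 5.3 pools both control types for perinatal and neonatal outcomes without restricting or adjusting for delivery site

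*Combined protocol and SAP*

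**What the plan says.** All references are to Version 1.8 unless stated otherwise.

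- **Retrospective controls (3.2.3.2, item 9).** They are excluded for "Delivery at a site other than one of the study centers or associated hospitals".
- **Sequencing group (3.2.1.2).** None of the 11 exclusions concerns place of delivery; the list ends with "Previous consent to the unsequenced prenatal group or enrollment in a previous pregnancy".
- **Prospective controls (3.2.2.2).** None of the 10 exclusions concerns place of delivery.
- **Amendment history.** For 3.2.1.2 and 3.2.2.2 it records "Updated exclusion criteria to eliminate the need for delivery at a study center or associated hospital". This is background only, but it shows that outside deliveries are admitted on purpose in those two groups.
- **Comparison (5.3).** The plan is that "pregnancy and neonatal outcomes will be compared among the prenatal sequencing group and the unsequenced prenatal group (prospective and retrospective"). No delivery-site restriction is given. Twelve-month outcomes are limited to participants enrolled prospectively.
- **Adjustment (5.3).** At the outset, "demographic data and severity of ultrasound findings will be compared to ensure there are no significant differences between the two study groups"; covariates enter the analysis only if differences are found. Delivery site is not named.
- **Cost (5.1).** Utilization and cost cover only women who deliver at a study center, and "power estimates assume cost will be available on 500 of the 750 in the prenatal sequencing group". Of the 350 controls, 15% are assumed lost to a causal microarray finding or to delivery elsewhere, leaving about 300.
- **Retrospective share (1.1).** Described only as a portion of the controls; no number is given.

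**The concern.** A selection rule on place of delivery applies to one part of the control group and to no one else. The plan handles this for cost, by taking study-center deliveries in every group, but not for the secondary outcomes through discharge in 4.10.2: gestational age at delivery, mechanical ventilation, sepsis, ECMO, other major morbidities, length of the initial NICU stay and death by discharge.

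If the risk of any of these differs between study-center and outside deliveries, for whatever reason, the difference in site mix will show up as a difference between sequenced and unsequenced pregnancies even when sequencing has no effect. A reader could take such a difference as evidence for or against prenatal sequencing.

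**Working it through.** **1. The plan's own figures.**

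- Sequenced pregnancies without cost data: 750 - 500 = 250, and 250/750 = 33.3%. Section 5.1 attributes this to referrals who deliver elsewhere.
- Controls kept: 350 x 0.85 = 297.5, matching the stated 300 or so.
- Power for charges, the only between-group power figure in Version 1.8: CV = 389,484/277,902 = 1.4015. The log-scale SD is sqrt(ln(1 + 1.4015²)) = 1.0424. With 500 versus 300, a ratio of 0.80 and two-sided alpha of 0.05, power is 83.4% for a log-scale test and 81.7% with the Mann-Whitney efficiency 3/π. The stated 80% is reproduced and slightly conservative. It does not bear on the argument here, except that it identifies the 500 versus 300 set.

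**2. Off-site share by group.** Let f be the retrospective share of the controls and q the off-site share among prospective controls. Neither is stated.

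- Sequenced: p_S = 1/3, the planning figure from step 1.
- Pooled controls: p_C = (1 - f) x q, since retrospective controls contribute none by rule.

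I vary f and take q as 15% or 33.3%. The 15% is the control loss in 5.1, which also includes causal microarray findings; the 33.3% assumes the same behavior as the sequenced group.

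**3. Spurious effect.** If the risk at study centers is R and the risk elsewhere is R - d, a group with off-site share p has risk R - p x d. With no effect of sequencing:

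- difference = (p_S - p_C) x d in absolute value
- risk ratio = (R - p_S x d)/(R - p_C x d)

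For d = 10 points the difference runs from 0 (p_C = 1/3) to 3.3 points (p_C = 0).

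**4. Illustration.** Assume R = 40% and d = 20 or 10 points, that is, 20% or 30% elsewhere. These rates are not in the documents.

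Sequenced: 40 - (1/3) x 20 = 33.3%, and 40 - (1/3) x 10 = 36.7%.

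| f | q | p_C | Control risk (d = 20; d = 10) | Spurious risk ratio |
|---|---|---|---|---|
| 1 (or q = 0) | any | 0% | 40.0%; 40.0% | 0.83; 0.92 |
| 0.75 | 33.3% | 8.3% | 38.3%; 39.2% | 0.87; 0.94 |
| 0.5 | 15% | 7.5% | 38.5%; 39.3% | 0.87; 0.93 |
| 0.5 | 33.3% | 16.7% | 36.7%; 38.3% | 0.91; 0.96 |
| 0 | 33.3% | 33.3% | 33.3%; 36.7% | 1.00; 1.00 |

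If outside deliveries carried the higher risk, d would be negative and the ratios would lie above 1.

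**The case against.** Several objections have force.

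- **The controls are not drawn from study centers alone.** A reader might infer that sequenced pregnancies from any hospital are set against controls from tertiary centers only. The documents do not support that. Prospective controls may deliver anywhere and are pooled with the retrospective ones, 5.1 itself expects some controls to deliver elsewhere, associated hospitals are permitted, and no passage calls the permitted sites tertiary. The first row of the table is therefore a limit and not the planned contrast.
- **The one-third is a weak input.** It is a planning figure for cost availability. It stands unchanged from Version 1.0, where planned delivery elsewhere was still an exclusion for the sequencing group, so it does not measure off-site delivery under the current criteria.
- **The direction is not established.** It is tempting to say that outside deliveries are milder and that the bias favors sequencing. Nothing in the documents says that delivery at a study center tracks severity.
- **Severity is already checked.** Section 5.3 compares ultrasound severity and adjusts if it differs. This helps, but it is conditional on an observed difference, and delivery site may carry risk that ultrasound severity does not capture.
- **Restricting conditions on a later event.** Delivery site is settled after results return, and section 2.1 expects results to guide delivery plans. Restriction can thus introduce selection of its own. This stands as a caution. It is not a reason to leave the asymmetry alone, because the plan already conditions on delivery site for retrospective controls and for cost. It is the reason to pair the restricted comparison with an all-deliveries one.

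**Conclusion.** The point holds in a limited form. As written, 5.3 compares groups selected under different delivery-site rules and has no step that deals with it. Site mix can confound the perinatal and neonatal comparisons through discharge.

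The size depends on quantities the documents do not give. Under the assumed rates and a one-third off-site share in the sequenced group, the spurious risk ratio is at most 0.83-0.92, with no control delivering off-site. It is about 0.87-0.96 with half the controls retrospective. It is close to 1 if few are retrospective and prospective controls deliver elsewhere as often as sequenced pregnancies. The retrospective share is probably not small: section 1.1 describes prospective control enrollment as limited, and the amendment history gives its infeasibility as the reason for adding retrospective controls.

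The scope is secondary outcomes for which the plan claims no power. A reader should not extend the point to the charges primary outcome, which is limited to study-center deliveries in all groups, or to the variant-yield primary outcome, which uses no controls. Twelve-month outcomes involve no retrospective controls.

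**What to change.** Amend section 5.3 as follows.

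1. Whenever retrospective controls are included, compare perinatal and neonatal outcomes through discharge among study-center or associated-hospital deliveries in all groups.
2. Also report the same outcomes for all deliveries, sequenced against prospective controls only. Neither of those groups is selected on delivery site.
3. State that delivery site may itself be influenced by sequencing results, so the two analyses are to be read together.
4. Report the number and share of off-site deliveries in each of the three groups, so that the imbalance is visible.

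The change is to analysis wording. By the plan's own figures the restricted comparison has about 500 versus 300 instead of 750 versus 350. Those numbers are approximate, because 5.1 speaks of study centers only and does not mention associated hospitals. The price is about a third fewer sequenced pregnancies in the restricted comparison, and a prospective-only analysis that may be imprecise given limited prospective control enrollment.

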# 4 Study Procedures

# 4.1 Screening for Eligibility and Consent

Eligible patients with specified fetal structural anomalies will be identified by prenatal ultrasound and/or fetal MRI. Center investigators and their staff in the outpatient ultrasound prenatal diagnostic units will be responsible for identifying eligible patients. To maximize recruitment, coordinators at each center will screen the prenatal diagnostic logs on a daily basis to identify eligible patients.

Upon recognition of a specified fetal anomaly, the maternal fetal medicine physician (MFM)/ ultrasonographer and/or a genetic counselor will explain the ultrasound finding as per routine clinical care. At the conclusion of the initial evaluation/consult, women will be informed by the physician/counselor and/or coordinator about the study. Once the potential participant indicates willingness to hear more about the study, a study coordinator will meet with the parents, review eligibility, and explain the study. Women who choose to undergo prenatal invasive testing will be approached for the prenatal sequencing group but will not be enrolled until a negative or non-causal karyotype/CMA is confirmed (with the exception of those enrolled into expedited prenatal sequencing, section 4.2.1). Women who choose not to have any diagnostic testing or decline sequencing will be approached for participation in the unsequenced prenatal group. A portion of the unsequenced group will be enrolled through medical record review under a waiver of consent. All women with a specified fetal anomaly will be recorded on a screening log that collects screening ID, date screened, planned invasive prenatal testing, ultrasound anomaly, screening status code and reason for study ineligibility (if applicable). A participant flowchart is shown in Figure 1.

Figure 1. Prospective screening flowchart

#### 4.1.1 Informed consent

Signed informed consent must be obtained from participants and the genetic father of the fetus prior to any study procedures for prospective enrollment. Three consents may be employed for this study:

- Short consent for potentially eligible women in the prenatal sequencing group that allows for collection of study samples prior to determination of the CMA and karyotype result. If CMA/karyotype results come back negative, eligible participants will sign the full study informed consent form to proceed with sequencing.
- Full study consent for the prenatal sequencing group that describes the specific group's participation in the study and risks
- Full study consent for the prenatal unsequenced group that describes the specific group's participation in the study and risks

Participants in both the sequenced and unsequenced groups will be assured that their participation in the study is purely voluntary and that patient care will not be affected if they decline participation in the study. Patients who are not fluent in English will be enrolled by a person fluent in Spanish. Both verbal and written informed consent and authorization will be obtained in that language; if this is not possible the patient will be excluded.

Enrollment of participants in the retrospective unsequenced prenatal group will occur under a waiver of consent.

#### 4.2 Enrollment

# 4.2.1 Prenatal sequencing group

For the prenatal sequencing group, chorionic villus sampling (CVS) or amniocentesis will be performed per standard of care. For twin gestations, either the twin with the anomaly or both twins will be sampled according to local clinical practice. For CVS sampling, a portion of the villi, cultured villi or extracted DNA will be sent to the sequencing laboratory. For amniocentesis, the usual draw of 40cc of fluid will be divided by the cytogenetics lab, with a portion used for clinical testing (minimum standard amount as per diagnostic laboratory practice) and from the remainder, DNA will be extracted for sequencing in a CLIA laboratory. Additional DNA for sequencing will be extracted from the cultured cells and the sequencing lab will determine which is the optimal source for sequencing, after quality and quantity verification. Amniotic fluid supernatant will be kept for future research.

Potentially eligible participants will sign either the screening consent form or study consent form prior to collection of parental samples. Thirty ml of maternal blood or buccal swab/saliva will be collected for sequencing and future research; future research will include investigating non-invasive prenatal testing (NIPT). Paternal blood (up to 10 ml) or buccal swab/saliva will be collected for sequencing and future research. Every effort will be made to obtain samples from both parents prior to or at the time of the diagnostic procedure. If the father is absent, a sample will be obtained as soon as possible. If no paternal sample is obtained, the participant will be classified as a screen failure and will not be enrolled into the study. The parental samples will be sent for DNA extraction as soon as they become available.

If the clinical karyotype, CMA or any other non-sequencing test result is known to be positive prior to sequencing, and felt to be causative of the anomaly, the karyotype/CMA results will be recorded, the participant will be classified as a screen failure and not enrolled, and parental samples/DNA will be discarded.

If the clinical karyotype/CMA results are negative (or non-causative), eligibility criteria will be confirmed, the participant and genetic father will sign the study consent form (if not already signed),

either in person or electronically, parental samples will be collected if needed, and genome sequencing will proceed. This defines the time enrolled in the study. Parents declining participation at this time will be considered as having refused consent; these participants may be offered participation in the unsequenced prenatal group if eligibility criteria are met. Those choosing to terminate their pregnancy based on ultrasound/CMA findings are ineligible.

